# 1016 **5.2.2 Unblinding Procedure**

After verification under blinded status, the data will be locked and unblinded. The statistician will be informed of the drug names corresponding to the drug codes to perform statistical analysis for all data. The unblinding documents will be signed jointly by the principal investigators, sponsors, CROs, and statisticians.

# 1026 ADVERSE EVENTS AND SERIOUS ADVERSE EVENTS

# 1022 **6.1 Adverse Events**

#### 1023 **6.1.1 Definition of Adverse Events**

- 1024 Adverse Events refer to all adverse medical events that occur after subject receives the IMP, 1025 which can be manifested as symptom signs, diseases or abnormal laboratory tests, but are not 1026 necessarily causally related to the IMP. In this trial, safety information should be collected from 1027 the time the subject signs informed consent until the last follow-up visit. Clinical AEs occurring 1028 after the signing of informed consent and prior to the first dose of drug are recorded in the 1029 original medical record as medical history/concomitant illnesses and are not recorded as AEs, but 1030 injuries/damages resulting from clinical trial investigations are required to be recorded as AEs. 1031 Any clinical abnormality that occurs during the time period starting from the first dosing and the 1032 last clinic follow-up visit that is judged by the clinician to be clinically significant, regardless of 1033 whether it is causally related to the trial drug or not, is judged to be an adverse event. Laboratory 1034 test abnormalities without clinically significant are not documented as AEs or SAEs.
- 1035 AEs include but not limited to the following:
- 1036 A. Newly diagnosed disease;
- 1037 B. Abnormal laboratory test result with clinical significance, and/or associated with
- 1038 concomitant symptoms;
- 1039 C. Clinically significant symptoms and signs;
- D. Clinically significant findings (e.g., physical examination, ECG, etc.);
- 1041 E. Exacerbation of pre-existing disease, symptoms, signs, or laboratory abnormalities;
- F. Allergy.
- 1043 **6.1.2** Access to Adverse Events
- 1044 The investigator should report all AEs directly observed or spontaneously reported by the
- subjects. In addition, investigators are required to regularly inquire about AEs from the
- participants after the initiation of this trial.
- 1047 **6.1.3 Recording of adverse events**
- Adverse event record forms should be completed faithfully during the trial period (after the first
- dosing to the last follow-up visit), including the time of occurrence, severity, duration, measures

- taken and outcome of the adverse event. AEs should be recorded in the designated adverse event
- form in the original medical record and case report form.
- The adverse event should be named in medical terminology, and prefer using medical diagnosis.
- That is, multiple signs, symptoms, and laboratory abnormalities can be called or attributed to a
- disease or impairment, then this is treated as an adverse event. Symptoms/signs will be used if
- the diagnosis cannot be made definitively. When the diagnosis is clear at a later stage, the record
- should be updated to replace the previous symptoms/signs with the diagnosis.
- 1057 When determining the names of AEs, ensure that each adverse event name consists of a single
- event. One diagnosis, sign/symptom is one adverse event. Therefore, when a subject presents
- with symptoms of "vomiting and diarrhea," the adverse event name should be recorded as two
- 1060 AEs, e.g., (1) diarrhea and (2) vomiting, rather than one "diarrhea and vomiting" for both
- symptoms. If the laboratory test abnormality is part of a syndrome, record the syndrome or
- diagnosis (e.g., anemia) rather than the laboratory test result (i.e., decreased hemoglobin).
- AEs are recorded according to the latest edition of the International Medical Dictionary for
- 1064 Regulatory Activities (MedDRA) as "System Organ Class (SOC)" and "Preferred Term
- 1065 (PT)". "Preferred Term (PT). Describe the number of cases, number of occurrences and incidence
- of all AEs, all TEAEs, TEAEs related to IMP, serious TEAEs, serious TEAEs related to IMP,
- TEAEs leading to withdrawal from the trial, TEAE-related deaths, etc., according to treatment
- 1068 group.

#### **Duration of Adverse Event Collection**

- 1070 In this trial, safety information should be collected from the time the subject signs informed
- 1071 consent until 14 days after the last dosing.

# 1072 **6.1.4 Follow-up of unresolved adverse events**

- All AEs and serious AEs for each subject should be actively followed up throughout the study.
- All events should be followed up until resolved, or the subject's conditions are stable, or the
- cause of the event has other explanations, or the subject is lost to follow-up, even if the event
- 1076 persists after discontinuation of treatment or termination of the study. As long as there is a
- medical indication, the investigator should follow up any AEs that were not resolved at the time

- of the last visit, but the follow-up not need to be recorded in the eCRF.
- 1079 The sponsor reserves the right to request more information (if necessary) from any subject
- regarding the ongoing AEs/serious AEs after the end of the study.

# 1081 **Post-study event**

- After the end of the last visit or permanent suspension of the study, the investigator is no longer
- obliged to inform the sponsor of new AEs or serious AEs occurred in subjects after the safety
- 1084 follow-up. However, the investigator should inform the sponsor's pharmacovigilance team or
- representative if the investigator is informed of any serious adverse event (including death) that
- has occurred after the subject has permanently withdrawn from the study and there is reasonable
- reason to believe that the event may be related to the investigational product.

# 1088 Variable

- The following variables will be collected for each adverse event (AE):
- 1090 (1) AEs (written records);
- 1091 (2) The start and end dates of AEs;
- 1092 (3) The severity grade according to CTCAE 5.0;
- 1093 (4) Whether it is a serious adverse event (SAE);
- 1094 (5) The causal relationship between the AEs and the IMP assessed by the investigator;
- 1095 (6) Measures taken on IMP;
- 1096 (7) Treatment for the AE;
- 1097 (8) Outcome of the AE.

# 1098 In addition, the following variables will be collected from each serious adverse event:

- 1099 (1) The date of the adverse event meets the criteria for the SAE;
- 1100 (2) The date of the investigator is informed of the SAE;
- 1101 (3) The cause of the SAE;

Version 1.1 / Jul 29, 2020 *confidential* Page 52 of 91

- 1102 (4) Date of discharge;
- 1103 (5) Possible causes of death;
- 1104 (6) The date of death;
- 1105 (7) Autopsy (if any);
- 1106 (8) Assessment of causality between SAE and research operations;
- 1107 (9) Assessment of causality between SAE and other medications;
- 1108 (10) Description of the SAE.
- 1109 **6.2 Serious Adverse Events**
- 1110 **6.2.1 Definition of Serious Adverse Events**
- 1111 According to the ICH, a SAE refers to events that have caused one of the following damages
- after the use of IMP:
- 1113 (1) Death;
- 1114 (2) Life-threatening (Subjects face the risk of death when an event occurs. It does not refer to
- events that theoretically may lead to death if exacerbated);
- 1116 (3) Permanent or severe disability or loss of function;
- 1117 (4) Hospitalization or prolongation of existing hospitalization;
- 1118 (5) Congenital anomalies or birth defects;
- 1119 (6) Other important medical event.
- Other important medical events: Medical and scientific judgment should be exercised in deciding
- whether to speed up reporting on other situations. Important medical events may not immediately
- endanger life, lead to death or hospitalization, but if medical measures are needed to prevent one
- of the above situations, it is usually considered to be serious. Example of such events include
- important treatment in the emergency room or allergic bronchospasm or convulsions occurring at
- home or resulting in drug dependence or abuse, etc.

# 1126 Suspected Unexpected Serious Adverse Reaction (SUSAR)

- 1127 SUSAR means the suspected and unexpected serious adverse reaction whose clinical
- presentation is of a nature and severity that exceeds the information available in the investigator's
- brochure for the IMP. The definition of predictability of AEs will be judged based on whether
- they are listed in the investigator's brochure.

# 1131 **Hospitalization**

- 1132 AEs during the study leading to hospitalization or prolongation of existing hospitalization are
- attributed to SAEs (the reason for this event should be due to AEs, not due to selective surgery,
- 1134 non-medical reasons, etc.). Any new medical facility hospitalization (even if the time of
- 1135 hospitalization is less than 24 hours) meets this standard. Hospitalization also includes
- in-hospital transport to emergency/intensive care unit (e.g. from department of internal medicine
- transport to coronary care unit, from neurology department transport to tuberculosis ward, etc.).
- Hospitalization does not include the following situations:
- 1139 (1) Rehabilitation institutions;
- 1140 (2) Hospice care institutions;
- 1141 (3) Short-term care institutions (e.g. nursing care);
- 1142 (4) Professional nursing institutions;
- 1143 (5) Nursing home;
- 1144 (6) Admission to the regular emergency department;
- 1145 (7) Day surgery (outpatient/day surgery/daytime operation).

#### Hospitalization or prolonged hospitalization due to the following reasons is not a SAE:

- 1147 (1) Hospitalization due to progression of pre-existing disease that unrelated to new AEs (for
- example, an examination of an abnormal laboratory test that has been performed prior to
- 1149 treatment);
- 1150 (2) Hospitalization for non-medical reasons (e.g. the subject is homeless);

- Protocol No.: MP-2019-004
- 1151 (3) Transactional hospitalization (e.g. annual medical examination);
- 1152 (4) Hospitalization as planned by the clinical trial protocol (e.g., for the required operation of the
- clinical trial protocol);
- 1154 (5) Voluntary hospitalization that does not cause clinical AEs (e.g. for elective plastic surgery);
- 1155 (6) Pre-planned treatment or surgery for the entire clinical trial protocol and/or subject should be
- recorded in the baseline document;
- 1157 (7) Specially admitted to hospital for the use of IMP.
- 1158 **6.2.2** Severity assessment
- SAEs from severe adverse events need to be identified. An adverse event that is severe in
- severity is not necessarily a serious adverse event. For example, vomiting that lasts for several
- hours may be considered severe but is not a serious adverse event. On the other hand, a stroke
- that results in only minor functional impairment may be considered a mild stroke but is a serious
- adverse event.
- The investigator should assess the severity of each adverse event and serious adverse event
- reported during the study according to NCI-CTCAE v5.0.
- AEs not included in the standard are referred to the following criteria:
- 1167 Grade I: Mild; asymptomatic or mild symptoms; clinical or diagnostic observations only;
- intervention not indicated.
- 1169 Grade II: Moderate; minimal, local or noninvasive intervention indicated; limiting
- age-appropriate instrumental activities of daily living, which refers to preparing meals, shopping
- for groceries, using the phone, managing money, etc.
- Grade III: Severe or medically significant but not immediately life-threatening; hospitalization or
- prolongation of hospitalization indicated; disabling; limiting self-care activities of daily living,
- 1174 which refers to: bathing, dressing and undressing, feeding self, using the toilet, taking
- medications, etc., not bedridden.
- 1176 Grade IV: Life-threatening consequences; urgent intervention indicated.

- 1177 Grade V: Death related to adverse events.
- 1178 **6.2.3** Causality relation assessment
- The analysis of the correlation between AEs and the IMP requires comprehensive consideration
- of the following factors:
- 1181 (1) Whether there is a reasonable temporal relation between the AEs and the action time of the
- 1182 IMP;
- 1183 (2) Whether the AE disappears or resolves after the IMP is discontinued or the dose reduced;
- 1184 (3) Whether the clinical or pathological manifestations of the AEs are consistent with the known
- pharmacological and toxicological characteristics of the IMP;
- 1186 (4) Whether the adverse event can be explained by the subject's own clinical status,
- psychological factors, or other environmental factors.
- The investigator should evaluate the possible relationship among the AEs, the IMP, and
- concomitant medications according to the following five-level classification criteria:
- 1190 1) Definitely related: Occurrence of the reaction is in line temporally with the IMP
- administration, and the reaction is consistent with the type of reaction known for the IMP;
- the AE may have improved after discontinuing IMP, and recurred after resuming dosing.
- 1193 2) Probably related: Occurrence of the reaction is in line temporally with the treatment, the
- reaction is consistent with the known principles of the treatment, and cannot be explained by
- the subject's clinical status, psychological factors, or other environmental factors; the
- adverse event is resolved after the treatment is discontinued.
- 1197 3) Possibly related: Occurrence of the reaction is in line temporally with the IMP, the reaction
- is consistent with the type of reaction known for the IMP, and the subject's clinical status,
- psychological factors, or other environmental factors also could have caused the reaction.
- 1200 4) Unlikely related: Occurrence of the reaction is not in line temporally with the IMP, the
- reaction is not quite consistent with the type of reaction known for the IMP, and the subject's
- clinical status, psychological factors, or other environmental factors also could have caused

1204

1205

1206

1207

1208

1209

1213

Protocol No.: MP-2019-004

the reaction.

5) Not related: Occurrence of the reaction is not in line temporally with the IMP, the reaction is not consistent with the type of reaction known for the IMP, and the subject's clinical status, psychological factors, or other environmental factors also could have caused; the reaction resolved when the external conditions were improved, or when the treatment is discontinued.

# **Adverse Events Related to the Investigational Product**

	Definitely related	Probably related	Possibly related	Unlikely related	Not related
Reasonable time sequence with investigational product	+	+	+	+	-
Known types of drug reaction	+	+	+	-	-
Decrease or disappearance of the reaction after stopping the drug	+	+	±	±	-
Repeated reactions after re-administration	+	?	?	?	-
Cannot be explained by subject's disease	+	+	-	±	-

Note: + denotes affirmation, - denotes negation, ± denotes difficulty in affirmation or negation, ? indicates that the situation is unknown. Definitely related, probably related, possibly related, these three levels can be considered as adverse reactions caused by the drug.

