# **Secondary Endpoints:**

✓ Difference between the groups in the proportion of events such as death, tracheotomy, invasive ventilation, or continuous non-invasive ventilation ( $\geq 22$  h per day for  $\geq 10$  days);

	✓ Difference between the groups in gripe strength change from baseline at Day 180;
	✓ Difference between the groups in respiratory function (%FVC) change from baseline at day 180;
	✓ Difference between the groups in ALSAQ-40 scores change from baseline at Day 180.
	Safety evaluation including: adverse events (AEs), serious adverse events (SAEs), clinical laboratory tests (hematology, urinalysis, blood biochemistry, thyroid function), vital signs (blood pressure, respiratory rate, pulse and body temperature), 12-lead electrocardiogram (ECG) examination, physical examination.
	Primary safety indicators:
Safety Assessment Indicators	Percentage of subjects with serious adverse reactions within 180 days; (Adverse reactions: AEs related to the IMP)
	Secondary safety indicators:
	Percentage of subjects with adverse reactions within 180 days;
	AEs, SAEs, and their incidence, the clinical manifestations, severity, time of occurrence, end time, duration, treatment measures and outcomes of these are to be recorded, and the correlation between AE and IMP are to be determined.
PK/PD and Biomarkers	The cerebrospinal fluid (Tmax after administration, optional) is to be taken (in part of subjects) at baseline period before administration and 180 days after administration, and the concentration of TBN and its metabolites in cerebrospinal fluid and plasm are to be measured for PK/PD analysis. Biomarkers, such as 3-NT, 8-OHdG, NFL levels in cerebrospinal fluid are to be determined.
Treatment	Subjects need to terminate the treatment permanently if the following events occur:
Termination Termination	✓ The subject is pregnant;
	✓ The subject withdraws informed consent;
	✓ The subject has a medical emergency that requires to terminate the

	treatment permanantly, such as death, tracheotomy, invasive ventilator assisted ventilation, or continuous non-invasive ventilator assisted ventilation (≥ 22 h per day for ≥10 days);  ✓ The subject has a medical emergency requiring a unblinding of the treatment of the subject;  ✓ Determinations based on medical reasons made by investigator.

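### Section 6.2.3 ties every counted causality grade to a known type of reaction, so read literally the adverse-reaction percentages omit new types; separately, its text and table disagree on timing for unlikely related

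*Protocol*

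**What the plan says.** - **Indicator.** The Synopsis (Safety Assessment Indicators) names as primary safety indicator "Percentage of subjects with serious adverse reactions within 180 days; (Adverse reactions: AEs related to the IMP"). The percentage of subjects with any adverse reaction is a secondary indicator. Section 3.3.2 lists the same two percentages.
- **What counts.** The note under the section 6.2.3 table, headed Adverse Events Related to the Investigational Product, states: "Definitely related, probably related, possibly related, these three levels can be considered as adverse reactions caused by the drug".
- **Table.** The row "Known types of drug reaction" carries + for *definitely*, *probably* and *possibly related*, and - for *unlikely* and *not related*. The row on reasonable time sequence carries + for the first four grades and - only for *not related*.
- **Text of section 6.2.3.** *Definitely related*: "administration, and the reaction is consistent with the type of reaction known for the IMP". *Probably related*: "reaction is consistent with the known principles of the treatment, and cannot be explained by" the subject's condition or surroundings. *Possibly related*: "is consistent with the type of reaction known for the IMP, and the subject's clinical status" or other factors might also explain it. For the fourth grade: "Unlikely related: Occurrence of the reaction is not in line temporally with the IMP".
- **SUSAR paragraph (section 6.2.1).** A SUSAR is a suspected serious reaction whose nature and severity go beyond the investigator's brochure. "The definition of predictability of AEs will be judged based on whether" they appear in that brochure.

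**The concern.** There are two separate faults.

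First, the known-type condition works as a gate on every counted grade. Whether a reaction has been seen before is a question of expectedness; whether the drug caused this event is a question of causality. Section 6.2.3 lets the first decide the second. The SUSAR paragraph keeps them apart, because it presupposes that a suspected reaction can be of an unlisted kind.

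Second, the text and the table give opposite timing criteria for *unlikely related*. An investigator who uses one will not grade as a colleague who uses the other.

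This matters because experience with the drug is short. Section 1.2.4 says that no efficacy study of the tablets in patients had been carried out, and describes repeated tablet dosing in healthy volunteers over about a week. This trial doses patients with ALS for 180 days. Reactions of a new kind are part of what such a trial should be able to count.

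**Working it through.** No arithmetic applies: the protocol states no event rate or figure to reproduce. The check sets the text beside the table, grade by grade, and follows two events through both.

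| Grade | Counted? | Known type, table | Known type, text | Timing, table | Timing, text |
|---|---|---|---|---|---|
| Definitely | yes | + | required | + | in line |
| Probably | yes | + | looser: fits what is known of how the treatment works | + | in line |
| Possibly | yes | + | required | + | in line |
| Unlikely | no | - | not quite consistent | **+** | **not in line** |
| Not related | no | - | not consistent | - | not in line |

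**Event A:** serious, well timed, not explained by the disease, resolves on stopping, of a type not known for TBN.

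- *By the table.* Definitely, probably and possibly each fail on the known-type row. *Not related* fails on timing. *Unlikely* fits: timing +, known type -, and ± for both resolution on stopping and explanation by the disease. Event A is not counted.
- *By the text.* Definitely and possibly fail on known type. Unlikely and not related fail because both describe poor timing. Probably is open only if its looser wording is read more widely than the + in the table. Event A has no clear grade.

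**Event B:** serious, well timed, of a known type, but the disease could equally explain it.

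- Both text and table give *possibly related*. Event B is counted.

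So event A, with the stronger case for causation apart from novelty, is left out while event B is counted.

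**Effect on the comparison.** For a type treated as new, no arm contributes to either adverse-reaction percentage. On those two measures the difference between arms for that type is nil, whatever the true difference.

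**The faults are independent.** *Unlikely related* is uncounted in both text and table. Settling its timing criterion would bring no event into the indicator; only the known-type condition does the excluding. The timing conflict instead leaves event A without a clear text grade and invites inconsistent grading between sites.

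**The case against.** The strongest reply is that the trial does not depend on these grades to find a new toxicity. Most of that reply stands.

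- **All events are analysed.** The Synopsis also lists AEs and SAEs with their incidence among the secondary safety indicators, without a causality filter. Section 6.1.3 describes all treatment-emergent and serious treatment-emergent events by treatment group, and section 8.3.5 compares AEs and SAEs between groups.
- **Reporting does not stop at the investigator's grade.** Under section 6.3.1 SAEs go to the sponsor without a causality condition, apart from documented exceptions. Under section 6.3.2 the sponsor assesses relevance and expectedness itself, and other serious safety information has its own route. Section 9.4 adds a monitoring committee.
- **The text leaves room for judgement.** Section 6.2.3 asks for several factors to be weighed together, one being the drug's known pharmacology and toxicology. Known is not defined.

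A reader might therefore infer more than the documents support in four ways:

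- *That new toxicities go undetected, or that all safety indicators count only adverse reactions.* The unfiltered analyses contradict this.
- *That the SUSAR category is nearly emptied.* The sponsor is not bound to the investigator's table, and the definition also refers to severity, so a known type of reaction may still qualify.
- *That known means seen in the 128 healthy subjects of section 1.3.1, so that missed cases can be estimated.* The protocol nowhere says so. The animal findings it reports (nervous system, digestive system, thyroid) could be taken as known types. No numerical size follows.
- *That new types can never be counted.* That is the strict reading; the text of *probably related* is looser.

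What the reply does not remove is the table itself, which closes the *probably* route, and the direct conflict over timing. An undefined word that decides entry to the primary safety indicator is also a weakness rather than a safeguard.

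**Conclusion.** Both faults are established from the page. Read literally, the table keeps a well-timed reaction of a new type out of every counted grade, and the text does so for *definitely* and *possibly related*. The percentages with serious adverse reactions and with any adverse reaction are then undercounted, and the rule conflicts with the SUSAR definition. Separately, text and table contradict each other on timing for *unlikely related*.

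The damage is confined to those two percentages and to investigator causality grading. The direction is certain on the literal reading; the size cannot be stated, because it depends on how often new types occur and on how investigators understand known. The conclusion assumes that sites apply the table as printed. An amendment is justified because the rule produces a wrong count in the named primary safety indicator and is cheap to correct.

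**What to change.** 1. In section 6.2.3, remove known reaction type as a necessary condition for *possibly related*, in both text and table; for example, set that table cell to ±.
2. Make text and table state the same timing criterion for *unlikely related*, so that a well-timed event of a new type has one clear grade.
3. Check both against the SUSAR paragraph, so that an event can be related and yet unlisted. While doing so, bring the text and table for *probably related* into agreement on known type.

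The primary safety comparison need not change; the unfiltered comparison of all AEs and SAEs by arm is already planned.

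The cost is an amendment to one table and two definitions, with some site retraining. More events will be rated *possibly related*, and more expedited reports will follow.
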